3.2.3 Per-Protocol Set (PPS)

The Per-Protocol Set is defined as all subjects in the FAS except for those who are excluded because of major protocol deviation. A major protocol violation is one that may affect the interpretation of study results. The criteria of major protocol deviations may include but is not limited to deviation from:

- A patient who does not have primary endpoint value.
- Any major violations of efficacy-related entry criteria.
- Deviation of an inclusion or exclusion criterion.

Major protocol deviations will be reviewed case by case on a regular basis during the conduct of the study by the Medical Monitor and clinical trial management team and adjudicated before database lock.

3.2.4 Safety Population (SAF)

The safety population is defined as all subjects who sign the ICF and are treated with the investigational treatment; these subjects are considered evaluable as the safety population.

3.3 Demographics and Baseline Characteristics

All variables concerning demographic, and baseline characteristics will be summarized by cohort, relative autograft mesh ratio group at the SOMA Tx site (m+1 and m+2) and all subject to describe the study population. Continuous variables will be summarized by number of subjects (n), mean, standard deviation, median, minimum and maximum. Categorical variables will be summarized by frequency and percentage. Summaries will be presented for all subjects in the FAS populations.

Confidential and Proprietary

3.4 Medical History

Medical history terms will be coded using the Medical Dictionary for Regulatory Activities (MedDRA), version 23.0. The frequency and percentage of subjects with medical history within each system organ class will be summarized by all subjects and by cohort, and relative autograft mesh ratio group at the SOMA Tx site (m+1 and m+2).

3.5 Prior and Concomitant Medications

Prior and concomitant medications will be coded using the WHODRUG dictionary B, version September 2019 (i.e., WHODDSEP19B3). The frequency and percentage of subjects with prior and concomitant medications by using Anatomical-Therapeutic-Chemical (i.e., ATC 4) classification and preferred term name will be summarized all subjects and by cohort, and sites.

3.6 Treatment and Exposure

The number of subjects with sites allocated to AG Tx and SOMA Tx in Cohort 1 and Cohort 2 and their autograft mesh ratio will be summarized. The size of area treated with AG Tx, SOMA Tx, AG donor and SOMA donor will also be summarized with the area categories of up to 400 cm² or 400 to 1,900 cm². The treatment placement location and position, and treatment measurements will be summarized by cohort and sites.

The duration from Day 1 to the end of study will be summarized by cohorts, sites and all subjects.

3.7 Efficacy Analysis

Efficacy analyses will be performed comparing the differences between treatments within subjects, where appropriate. Descriptive summaries will be reported by treatment site, relative autograft mesh ratio group at the SOMA Tx site (m+1 and m+2), cohort and all subjects.

For continuous variables, descriptive statistics will include the following: the number of patients reflected in the calculation (n), mean, median, standard deviation, minimum, and maximum.

For categorical or ordinal data, frequencies and percentages will be displayed for each category. The definition of primary and secondary endpoints is described in Section 2.2.1 and 2.2.2.

Safety assessments will include monitoring of TEAEs, vital signs, laboratory safety values, incidence of wound infection-related events, and potential immunologic responses to StrataGraft.

Confidential and Proprietary

3.7.1 Co-Primary Endpoints Analysis

There is no formal hypothesis test for primary efficacy variables. All p-values provided in the tables are considered as screened p-values for signal exploration.

The primary efficacy analysis will be performed on the FAS and PPS (details in Section 3.2.2 and 3.2.3, respectively). If the difference in the number of subjects between the FAS and the PPS is less than or equal to 2, no analysis will be performed on the PPS.

For the first co-primary endpoint, which is the calculated percent reduction of donor skin (as defined by [1-(AG Tx total mesh ratio/SOMA Tx total mesh ratio) × 100]) harvested at Month 2, the Wilcoxon Signed Rank test will be used.

If autografting occurs by Month 2 at either treatment site, the total autograft mesh ratio with additional re-autografting is calculated as follows:

The total autograft mesh ratio is calculated as $1/(1/mr_0+p \text{ area}\%/mr_1)$.

Where:

- mro is initial mesh ratio
- mr1 is re-graft mesh ratio
- p_area% is percent wound area autografted after initial study treatment (additional autografting).

In addition, the areas of treatment and donor sites will be summarized by treatment site and by relative autograft mesh ratio group at the SOMA Tx site (m+1 and m+2).

For the paired binary 2nd co-primary endpoint of the difference in percent of SOMA Tx sites and AG Tx sites with confirmed complete wound closure without additional autografting at Month 2, 95% confidence intervals (CIs) of difference are derived by fitting a repeated measures model with PROC GENMOD that adjusts for the correlation with pairs, and then the 95% CI of difference can be estimated using the Margins Macro, provided by SAS. The P-value will be derived from McNemar's test.

The descriptive statistics will also be determined by treatment site and by relative autograft mesh ratio group at the SOMA Tx site (m+1 and m+2). The missing binary data will be imputed as non-responders.

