2.2.1 Efficacy Primary Objective and Co-primary Endpoints

The primary efficacy objective is to evaluate the efficacy of SOMA treatment by assessing two co-primary efficacy endpoints. The definitions of the two co-primary efficacy endpoints are as follows:

- Calculated percent reduction of donor skin (as defined by [1-(AG Tx mesh ratio/SOMA Tx mesh ratio)× 100]) at Month 2.
- Difference in percent of SOMA Tx sites and AG Tx sites with confirmed complete wound closure without additional autografting at Month 2.
 - Confirmed complete wound closure is defined as complete skin reepithelialization without drainage confirmed at 2 visits at least 2 weeks apart but
 no later than Week 20. Complete wound closure will be considered to have
 occurred at the earlier of the two observations of complete skin reepithelialization without drainage.
 - Confirmed complete wound closure without additional autografting at Month 2 is determined by Mallinckrodt's biostatistics and programming team based on the above definition. The first wound closure needs to have occurred before Month 2.

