2.2.7 Modification from the Statistical Section of the Final Protocol

The amendments to the statistical section and relevant endpoints of the final protocol are displayed here. The final analyses are based on this final SAP. The amendments are as follows:

In protocol section 4, objectives and endpoints (p. 19):

The exploratory endpoint, "Effect of total wound burden on rate of wound closure," is listed. However, no data has been collected on overall donor site closures. Consequently, no analysis will be performed for this endpoint.

- The protocol does not mention the endpoint 'Time to First Confirmed Wound Closure
 Without Additional Autograft by Month 2.' (see Section 2.2.3) However, this endpoint and
 its results were outlined in the briefing document (see the References: Type B Meeting
 Briefing Materials submitted in IND 010113 Sequence 0151 on 27 November 2023),
 leading to its inclusion.
- In protocol section 10.3.2 Efficacy Analyses (p36):
 The original analyses for the first co-primary endpoint as stated in the clinical protocol were as follows:

For calculated percent reduction of donor skin (as defined by [1-(AG Tx mesh ratio/SOMA Tx mesh ratio) × 100]) at Month 2, the log-transformation of the endpoint will be performed, and geometric mean ratio percent reduction of donor skin between treatment site will be presented.

A mixed-effect model repeated measures method with covariates, including subject treatment site, mesh ratio on SOMA Tx site, and cohort will be used for this log-transformed primary endpoint.

If the mixed-effect model repeated measures model does not converge or violates the model assumptions, the paired t-test will be used. If parametric statistics models are not appropriate, the Wilcoxon signed-rank test will be performed.

The updated statistical analysis will not use log-transformation, to facilitate easier clinical interpretation. Additionally, the mixed-effect model for repeated measures will not be used due to the small number of subjects and the existence of only one cohort. To ensure robustness of the method, the non-parametric Wilcoxon signed-rank test, as originally planned last method, will be used (see Section 3.7.1).

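### The first co-primary endpoint is printed with × 100 inside the subtraction, is worded differently in SAP 2.2.1 and 3.7.1, and has a Wilcoxon p-value that mainly reflects the assigned mesh ratios

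*SAP*

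**What the plan says.** The formula stands in the protocol synopsis, Protocol 4 and 10.3.2, and SAP 2.2.1 and 3.7.1, and SAP 2.2.7 repeats it from the protocol. All of these place × 100 before the closing bracket.

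- **Definition.** SAP 3.7 states: "The definition of primary and secondary endpoints is described in Section 2.2.1 and 2.2.2". Section 2.2.1 gives "1-(AG Tx mesh ratio/SOMA Tx mesh ratio)× 100]) at Month 2". Section 3.7.1 gives "1-(AG Tx total mesh ratio/SOMA Tx total mesh ratio) × 100]) harvested at Month 2", and adds that the total ratio after re-grafting by Month 2 is 1/(1/mr0 + p_area%/mr1), where "p_area% is percent wound area autografted after initial study treatment (additional autografting" defines the area term.
- **Changes from the protocol.** SAP 2.2.7 introduces the protocol method with "The original analyses for the first co-primary endpoint as stated in the clinical protocol were as follows" and then says "The updated statistical analysis will not use log-transformation, to facilitate easier clinical interpretation". It also drops the mixed model. It has no entry for the total mesh ratio.
- **Test.** Section 3.7.1 says "harvested at Month 2, the Wilcoxon Signed Rank test will be used" and gives no null value. It also says "There is no formal hypothesis test for primary efficacy variables" and treats p-values as screening values.
- **Design.** SAP 2.1 assigns the SOMA site an autograft meshed 1 or 2 ratios wider than control. Thirteen subjects were randomized. SAP 2.5 reports that the first 10 closed at both sites by Month 2 without additional autografting.

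**The concern.** There are three problems, plus a small one of notation.

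1. Followed literally, the formula gives the wrong sign and size for a co-primary endpoint.
2. The section named as the definition does not mention re-grafting, while the analysis section counts it. If 2.2.1 is read as the initial ratio, the two sections disagree for any re-grafted site, and the list of modifications does not tell the reader which applies.
3. The signed-rank test asks whether the reduction differs from zero (assumed, since no null is stated). The assignment already makes it positive unless enough of the SOMA site is re-grafted. A very small screened p-value could be taken as an efficacy signal when it chiefly restates the assigned mesh.

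The notation point is that p_area% must enter as a fraction. SAP 3.7.3.2 reuses the same calculation.

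**Working it through.** **Inputs.** From the documents: the formulas above, 13 randomized subjects (SAP 2.1), no additional autografting in the first 10, and reductions of 35% (m+1) and 57% (m+2) (SAP 2.5). Individual control ratios, applied ratios and re-graft ratios are not given, so the mesh values below are illustrations.

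**The plan's own figures.** The 35% and 57% cannot be reproduced exactly without individual ratios. The intended formula is compatible with them: with an assumed five subjects per group and additive mesh steps, m = 1, 2, 2, 2, 3 gives 35.0% for m+1, and m = 1, 1, 2, 2, 2 gives 56.7% for m+2. The printed formula would need AG/SOMA = (1 - 35)/100 = -0.34 or (1 - 57)/100 = -0.56, which is impossible.

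**Step 1: bracket.** Printed value 1 - 100(AG/SOMA); intended value 100(1 - AG/SOMA).

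| AG to SOMA | Printed | Intended |
|---|---|---|
| 1.5 to 2 | -74.0 | 25.0% |
| 2 to 3 | -65.7 | 33.3% |
| 2 to 4 | -49.0 | 50.0% |

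The printed value is negative unless the SOMA ratio is at least 100 times the AG ratio.

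**Step 2: mesh ratio against total mesh ratio.** Take a 2 to 3 pair; the initial ratios give 33.3%.

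- 20% of the SOMA site re-grafted at 2:1: total ratio 1/(1/3 + 0.20/2) = 2.308, reduction 1 - 2/2.308 = 13.3%.
- 20% of the AG site re-grafted at 2:1 instead: total ratio 1/(1/2 + 0.20/2) = 1.667, reduction 1 - 1.667/3 = 44.4%.
- All 13 pairs 2 to 3, with the last three having that SOMA re-graft: mean (10 × 33.33 + 3 × 13.33)/13 = 28.7%, against 33.3%.

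Entering p_area as 20 instead of 0.20 would give a total ratio of about 0.10 instead of 2.31.

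**Step 3: what reverses a pair.** With additive mesh steps, no AG re-graft and the SOMA site re-grafted at 1:1, the sign changes when the re-grafted fraction exceeds 1/m - 1/(m+k), with k = 1 or 2.

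| Control m | m+1 | m+2 |
|---|---|---|
| 1 | 50.0% | 66.7% |
| 2 | 16.7% | 25.0% |
| 3 | 8.3% | 13.3% |
| 4 | 5.0% | 8.3% |

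**Step 4: exact two-sided signed-rank p.** Assumptions: all 13 subjects are in the FAS, the first 10 are positive (treated as assigned), the null is zero, there are no ties, and zeros are dropped. W- is the rank sum of the negative pairs.

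| Last three subjects | p |
|---|---|
| All positive (n = 13, W- = 0) | 2/2^13 = 0.00024 |
| One negative, no zero | at most 0.0215 (W- = 13) |
| One negative, one zero (n = 12) | at most 0.0342 (W- = 12) |
| One negative, two zeros (n = 11) | up to 0.0537 (W- = 11) |
| Two negative, no zero | 0.0012 to 0.168 (W- = 3 to 25) |
| Three negative | 0.0034 to 0.542 (W- = 6 to 36) |
| All zero, or absent (n = 10) | 0.0020 |

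An exact zero is possible: m = 2, SOMA at 4:1 and 50% re-grafted at 2:1 gives a total ratio of 1/(1/4 + 0.50/2) = 2. So p above 0.05 needs two or three negative pairs among the last three subjects, or one negative and two exact zeros.

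**The case against.** The bracket is a notation slip with one sensible reading. The positive figures in SAP 2.5 suggest that nobody computed the endpoint as printed, and programming specifications sit in a separate document. This limits the practical risk, but the SAP exists to pre-specify the analysis, and its formula for a co-primary endpoint is wrong.

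Initial ratios are set on Day 1, so the words at Month 2 in 2.2.1 may already imply that later grafting counts, and 2.2.7 points to 3.7.1 for the updated analysis. That reading is fair. Even so, 2.2.1 does not state it, and 2.2.7 does not record it. With no re-grafting in the first 10 subjects, the gap can affect at most three pairs.

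The Wilcoxon test is the protocol's named fallback, the switch is disclosed, and p-values are labelled as screening. Through the total ratio the test also has some content: it can register donor saving lost to re-grafting. All of this stands, and it is why the harm is to interpretation only. But a p-value driven chiefly by assignment is a poor signal even for exploration.

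Mesh ratios are discrete, so ties are likely. Allowing any tie pattern raises the one-negative maximum from 0.0215 to 0.0242 (n = 13) and from 0.0342 to 0.0386 (n = 12). Both stay below 0.05.

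Descriptive summaries by m+1 and m+2, and of donor areas, are already planned in SAP 3.7 and 3.7.1, so the extra work is small.

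**Conclusion.** The concern holds and should be fixed. The formula is wrong as written wherever it appears: a 2 to 3 pair gives -65.7 instead of 33.3%. The two SAP definitions agree without re-grafting, but can differ by 20 percentage points for one pair in the illustration (33.3% against 13.3%). The p-value is not wholly fixed, because re-grafting in the last three subjects can move it. It is 0.00024 if all 13 pairs are positive, and it exceeds 0.05 only under the patterns in the last step of the check. These p-values rest on a null of zero and on the first 10 subjects having been treated as assigned. Confidence is high that the bracket is wrong and that the wordings differ. Whether the total ratio was a change or always the intention cannot be settled from the documents. No confirmatory claim is affected.

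**What to change.** - In SAP 2.2.1 and 3.7.1, define the endpoint as [1 - (AG total mesh ratio/SOMA total mesh ratio)] × 100, with p_area as a fraction from 0 to 1.
- Leave the quoted protocol formula in SAP 2.2.7 as it is. Add two entries there: the bracket correction, noting that the protocol has the same misprint, and the use of the total mesh ratio.
- Present the reduction descriptively by m+1 and m+2, with each subject's control m and any re-grafted area, beside closure without additional autografting.
- Either omit the Wilcoxon p-value, or keep it as the protocol's fallback with its null stated and a note that a positive sign is expected from the assigned mesh ratios and is not evidence that the overlay works.

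The cost is wording in three SAP sections, one table note and a subject-level listing from data already collected. Omitting the p-value would be a further departure made after the first 10 subjects' results were reviewed, and 2.2.7 would have to say so. Keeping it with the note avoids that.

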Following excision, a total of 20 subjects (Cohort 1) will be randomized into one of 2 groups, Group 1 and Group 2.

Following completion of the Day 28 assessments, each subject will be determined to be a success or failure based upon the criteria below:

- % closed at Day 28, with success declared if the difference between paired wounds
 10%, and
- Total score of Observer assessment of the POSAS at Day 28, with success declared if the difference between paired wounds < 20%.

Group success will be declared if \geq 80% subjects are determined to have treatment success within that group. Only one of the 2 SOMA Txs, m+1 or m+2, will be determined to meet the *a priori* established criteria above and become the SOMA Tx in Cohort 2.

Treatment Groups and Duration:

This study is open-label. Subjects will serve as their own control. Subjects will be randomized to receive autograft, meshed at a ratio per clinician judgment at 1 treatment site (m), and StrataGraft overlay of autograft at either m+1 (i.e., group 1) or m+2 (group 2), relative to the control autograft mesh ratio.

It is anticipated that each subject will participate in this study for up to 14 months: up to 2 weeks of screening followed by up to 12 months (± 4 weeks) of post-treatment observation.

Estimated Duration of Study

Enrollment ~36 months.

Duration of subject participation up to 60 weeks.

Total study duration ~96 months.

Study Was Terminated Early by Sponsor

Study enrollment was terminated on 12 January 2024 due to a decision to voluntarily discontinue sale and manufacture of StrataGraft for business reasons. A total of 13 subjects were randomized, all in Cohort 1, at the time of termination of enrollment. Follow up for enrolled subjects was completed in April 2024.

Scientific Rationale for Study Design

The current standard of care for closure of FT burns is autografting, i.e., the surgical harvest of healthy skin from an uninjured site and subsequent transplantation of the donor tissue to the wound following surgical excision of nonviable tissue from the burn. While this method is effective in achieving closure of the original wound, optimal sites for the harvest of donor skin are often limited, and closure of large areas of injury may necessitate sequential re-harvest of available donor sites. Additionally, the donor site is painful, susceptible to infection and scarring,

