2.5 Ad-hoc Data Review

Due to slow enrollment, the sponsor performed a preliminary assessment of the efficacy and safety of the product in April 2023 to determine the appropriateness of amending the ongoing Phase 1/2a StrataSOMA clinical study to a seamless Phase 1/2/3 study design. To this end, the sponsor performed an ad-hoc data analysis for the first 10 subjects enrolled in Cohort 1 after 1st 10 subjects completed primary endpoints assessments. Results of this data review were included

in Sponsor Meeting Materials for a Type B meeting with FDA to discuss the proposed clinical study amendment.

The ad-hoc data review demonstrated that all of the first 10 subjects enrolled in the StrataSOMA study achieved confirmed complete wound closure by or before Month 2 without additional autografting on both SOMA and AG treatment sites, regardless of whether they were randomized to the m+1 or m+2 group (i.e., 100% of the SOMA treatment sites achieved confirmed complete wound closure by or before Month 2 without additional autografting).

Additionally, SOMA treatment decreased the amount of donor tissue required to close treated sites relative to the control AG treatment site by 35% and 57% for autograft mesh ratios m+1 and m+2, respectively, without sacrificing cosmetic outcomes, as evidenced by comparable POSAS scores at Months 2 and 3.

For safety, ad hoc analyses of TEAEs or SAEs for the first 10 patients through the data cutoff showed that most TEAEs and SAEs were typical of what is observed in burn wounds and during wound healing. The safety profile at the StrataGraft treatment sites was similar to that of the control treatment sites, and no new safety signals were identified.

For details of the ad-hoc analyses, see the Type B Meeting Briefing Materials submitted in IND 010113 Sequence 0151 on 27 November 2023 (see References).

This ad-hoc data analysis will not alter the screened significance level of the entire study.

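### The planned confidence interval for the paired Month 2 closure difference has zero width or cannot be estimated when no pair is discordant, and the SAP gives no fallback

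*SAP*

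**What the plan says.** SAP 3.7.1 gives one interval method for the difference between SOMA and autograft sites in confirmed Month 2 closure: "95% confidence intervals (CIs) of difference are derived by fitting a repeated measures model with PROC GENMOD that adjusts for the correlation with pairs", with the difference and its limits then taken from the Margins macro. Neither the link nor the working correlation is stated. On the test it says "The P-value will be derived from McNemar's test", and on missing data "The missing binary data will be imputed as non-responders". It also says "There is no formal hypothesis test for primary efficacy variables" and treats p-values as screening values.

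Protocol 10.3.2 has the same interval method. Its fallback sequence (paired t-test, then Wilcoxon) belongs to the mixed model for the donor-skin endpoint. Its only conditional wording for the closure endpoint qualifies the McNemar p-value, and the SAP does not carry that over.

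Three other SAP sections bear on the point:

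- Section 2.1: "A total of 13 subjects were randomized, all in Cohort 1, at the time of termination of enrollment".
- Section 2.5: the first 10 subjects "achieved confirmed complete wound closure by or before Month 2 without additional autografting on both SOMA and AG treatment sites".
- Section 2.2.7, on the donor-skin endpoint: "the mixed-effect model for repeated measures will not be used due to the small number of subjects and the existence of only one cohort". No change is listed there for the closure endpoint.

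**The concern.** A GEE interval for a paired difference takes its width from the discordant pairs. When this SAP was finalized, the sponsor had already seen 10 pairs with none discordant, and at most three more could follow. The plan therefore relies on a method that may have nothing to work with, and it does not say what to report in that case.

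With formal testing set aside, estimation is the purpose of this analysis. The question is whether wider meshing plus overlay costs closure in exchange for the donor skin saved. The planned site counts and percentages carry no uncertainty. A printed interval of 0 to 0 would suggest that none exists, on 13 subjects at most. SAP 2.2.7 gives small numbers as a reason to drop the mixed model for the first co-primary endpoint, yet the second keeps a large-sample method on the same subjects.

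**Working it through.** The documents give no interval, power or sample-size figure for this endpoint, so there is none to reproduce.

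**Inputs.** 13 randomized (SAP 2.1); 10 of 10 closed at both sites (SAP 2.5); two-sided 95% limits (SAP 3.1), so z = 1.96. Let b be the number of subjects failing at the SOMA site only, c the number failing at the autograft site only, and n the number of pairs. n = 13 assumes all 13 are in the full analysis set.

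**Planned interval.** The estimate is (c - b)/n, with robust standard error √[(b + c) - (b - c)²/n] / n. If b = c = 0, this is 0 whatever the split between pairs closed at both sites and pairs failed at both. A subject imputed as a non-responder at both sites is also concordant, so the problem does not require 100% closure.

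Binomial GEE fits (statsmodels in place of SAS; logit and identity links; independence and exchangeable correlation) agree. Ten joint closures, 13 joint closures, and 12 joint closures plus one joint failure all gave zero width or a failed fit. With one to three SOMA-only failures the fits equalled the formula above.

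**Comparator.** The Tango score interval was solved numerically. With b = c = 0 its limits are ±z²/(n + z²):

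- n = 10: 3.84/13.84 = 27.8 points.
- n = 13: 3.84/16.84 = 22.8 points.

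As a cross-check, the exact 97.5% upper bound on a SOMA-only failure rate after 0 of 13 is 1 - 0.025^(1/13) = 24.7%.

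**Worked case, b = 1, c = 0, n = 13.** Estimate -1/13 = -7.7 points; standard error √(1 - 1/13)/13 = 0.0739; limits -7.7 ± 14.5, that is -22.2 to +6.8.

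| SOMA-only, autograft-only failures (n = 13) | Planned 95% CI, points | Tango 95% CI, points | Width ratio |
|---|---|---|---|
| 0, 0 | 0 to 0, or not estimable | -22.8 to +22.8 | 0 |
| 1, 0 | -22.2 to +6.8 | -33.3 to +16.9 | 57.7% |
| 1, 1 | -21.3 to +21.3 | -28.1 to +28.1 | 75.8% |
| 2, 0 | -35.0 to +4.2 | -42.2 to +10.9 | 73.8% |
| 2, 1 | -33.5 to +18.1 | -37.4 to +22.9 | 85.4% |
| 3, 0 | -46.0 to -0.2 | -50.3 to +5.0 | 82.9% |
| 4, 0 (only if a reviewed subject changes status) | -55.9 to -5.7 | -57.6 to -0.9 | 88.5% |

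The last row is included because the SAP's definition and its ad-hoc review differ slightly. SAP 2.2.1 requires "The first wound closure needs to have occurred before Month 2", while the review also counted closure at Month 2.

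**McNemar.** With no discordant pairs the asymptotic statistic is (b - c)²/(b + c) = 0/0, and the exact p is 1. At (3, 0) the asymptotic statistic is 9/3 = 3, p = 0.083; the exact p is 2 × 0.5³ = 0.25. The SAP does not say which version applies.

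**Coverage at n = 13**, enumerated exactly under assumed failure rates, with a zero-width interval counted as a miss unless the true difference is 0:

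| SOMA-only rate, autograft-only rate | Planned | Tango | No discordant pair |
|---|---|---|---|
| 5%, 0 | 48% | about 100% | 51% |
| 10%, 0 | 74% | 99.9% | 25% |
| 15%, 5% | 86% | 99% | 5.5% |
| 20%, 0 | 93.8% | 99.9% | 5.5% |
| 10%, 10% | 91.4% | 97.6% | 5.5% |

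**How likely is the degenerate case?** If each of subjects 11 to 13 is discordant with an assumed probability of 2% to 20%, all three are concordant with probability 0.98³ = 94% down to 0.80³ = 51%.

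**The case against.** The strongest reply is that the consequence is limited. Nothing is formally tested, enrollment stopped for business reasons, Cohort 2 never opened, and no decision rule uses this interval. That stands, and it keeps this from being a critical flaw. It does not make a zero-width interval an acceptable estimate.

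Second, the outcome is unseen. Subjects 11 to 13 may include a discordant pair, and SAS may report non-convergence instead of 0 to 0, in which case the interval is missing but not misleading. Both points are fair. The claim is conditional, and a missing interval with no stated substitute is still a gap.

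Third, SAP 3.7.2 plans exact binomial intervals for durable closure at Months 6 and 12, which keep their width at 100% closure. They are one-sample intervals at later times, so they do not estimate the paired Month 2 difference.

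Fourth, the planned method's coverage recovers as discordance becomes more common, and Tango is conservative here, so the width ratios overstate the planned interval's error. This also stands. Ten concordant pairs out of 10, however, make the low-discordance region the relevant one.

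Fifth, a single fallback sentence would cure the zero-discordance case without replacing the protocol's method, and any change now is made with 10 of the 13 outcomes known. A fallback alone would leave the over-narrow intervals at 1 to 3 discordant pairs. The data-informed timing should be disclosed.

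**Conclusion.** The concern holds and should be fixed. With no discordant pairs the planned interval is 0 to 0 or not estimable, while 13 concordant pairs remain compatible with a closure loss of about 23 points by the score interval. With 1 to 3 discordant pairs it is narrower than the score interval, and in the extreme case of 10/13 against 13/13 it excludes zero where the score interval does not. The unspecified McNemar version is a lesser point.

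This rests on four assumptions: the first 10 subjects keep their status under SAP 2.2.1; all 13 are in the full analysis set; SAS behaves like the GEE fits used here, giving either zero width or a failed fit; and the failure rates behind the coverage figures are illustrative. Confidence is high for the conditional statement. It does not extend to what subjects 11 to 13 will show.

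**What to change.** In SAP 3.7.1, replace the GENMOD/Margins interval for the second co-primary endpoint with a small-sample paired interval that stays defined when no pair is discordant. Either the Tango score interval or an exact unconditional interval would do; name one. Present it with the 2x2 table of SOMA closure by autograft closure, overall and for the m+1 and m+2 groups. If a screening p-value is kept, specify exact McNemar, reported as 1 when no pair is discordant. Record the change in SAP 2.2.7, saying that it was made after the first 10 subjects' results were known.

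The cost is SAP wording, one entry in SAP 2.2.7 and a few lines of code; no new data are needed. The price is a wider, somewhat conservative interval and one more departure from Protocol 10.3.2.
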